4.4 END OF STUDY DEFINITION

A participant is considered to have completed the study if he or she has completed all phases of the study including the last scheduled procedure shown in the Schedule of Activities (SoA), Section 1.3.

The end of the study is defined as completion of the last visit or procedure shown in the SoA in the trial globally.

5 STUDY POPULATION

5.1 INCLUSION CRITERIA

1. Men and women between 50 and 90 years of age, without a diagnosis of severe dementia
2. Carry a diagnosis of idiopathic Parkinson's disease based on the United Kingdom Parkinson's Disease Society Brain Bank clinical diagnostic criteria
3. Have had symptoms of Parkinson's disease for at least 3 years
4. Hospital's study-specific informed consent must be obtained
5. Must have capacity to provide informed consent in English
6. For female participants, confirmation that they have not had a menstrual period in over 12 months, or that they will use an effective form of contraception during the study

5.2 EXCLUSION CRITERIA

1. Inability to provide informed consent.
2. Severe dementia
3. History of epilepsy or brain surgery
4. Severe tremor or dyskinesia that would interfere with EEG as determined by the PI
5. Parkinson's patients with clinically significant medical or neurological conditions which may be an alternative cause of orthostatic hypotension, such as neuropathy, renal failure, heart failure, cardiac arrhythmias, severe diabetes, or spinal cord injuries
6. We will exclude patients who are treated with medications which can significantly lower blood pressure or heart rate, such as antihypertensive medications, diuretics, and alpha-blocking medications
7. Presence of other known central nervous system disease that may interfere with performance or interpretation of EEG or TMS
8. Presence of any implanted metal devices including, but not limited to, pacemakers, deep brain stimulators, vagal nerve stimulators, bladder stimulators, or cochlear implants.

5.3 LIFESTYLE CONSIDERATIONS

N/A

5.4 SCREEN FAILURES

Screen failures are defined as participants who consent to participate in the clinical trial but are not subsequently randomly assigned to the study intervention or entered in the study. A minimal set of screen failure information is required to ensure transparent reporting of screen failure participants, to meet the Consolidated Standards of Reporting Trials (CONSORT) publishing requirements and to respond to queries from regulatory authorities. Minimal information includes demography, screen failure details, eligibility criteria, and any serious adverse event (SAE).

Individuals who do not meet the criteria for participation in this trial (screen failure) because of availability for study visits or a concomitant medication that is subsequently stopped may be rescreened. Rescreened participants should be assigned the same participant number as for the initial screening.

5.5 STRATEGIES FOR RECRUITMENT AND RETENTION

Recruitment: Our sample for this study is 48 participants with Parkinson's disease age 50-90 years (See Sample Size Calculation). To recruit 48 participants, we will need to pre-screen 400 potential participants, and screen 90 potential participants, according to our experience in recruiting people with Parkinson's disease at our center. Participants will be recruited from among patients who are seen in neurology clinics at UNC for evaluation and treatment of idiopathic Parkinson's disease. A member of the research team will review data available in Epic for eligibility and recruitment, and flag patients who may qualify for the study. The treating neurologist will also be asked to consider potential participants' eligibility and ability to provide informed consent. Once potential participants have been identified, they will be asked in person, over telephone, and/or emailed by our research team to assess their interest in the study, and provide information about the research study. If the potential participant indicates they are interested, the study coordinator or research assistant will set up a time for the potential participant to have a screening research visit.

Retention: Retention strategies will include incentive payment upon completion of all study arms. Additionally, the research staff will call the participant at least 2 days prior to each study visit to remind them of the upcoming visit.

6 STUDY INTERVENTION

6.1 STUDY INTERVENTION(S) ADMINISTRATION

6.1.1 STUDY INVESTIGATIONAL PRODUCT

We will use the MagPro X100 system (MagVenture Inc., Alpharetta, GA, USA) for transcranial magnetic stimulation. The MagPro X100 is an advanced, high performance magnetic stimulator designed for research use. It is a high-quality product that allows a wide range of stimulation parameters. This stimulator allows selection of different waveforms, current direction, stimulation rates. It is easily connectable to external equipment via programmable input and output triggers. The system operates via a built-in computer, and is controllable from an external device.

6.1.1.1 SAFETY FEATURES

In the USA, federal law regulates the sale of Medical Devices through the US Food and Drug Administration (FDA). Devices which are permitted to be marketed for their intended use must have either a 510(k) or PMA clearance.

MagPro stimulators R20, R30, R30 with MagOption, X100, and X100 with MagOption are all FDA 510(k) cleared (k160280, K061645, K091940, and k150641).

k150641: The intended use is treatment of Major Depressive Disorder in adult patients who have failed to receive satisfactory improvement from prior antidepressant medication in the current episode.

k160280, K061645, K091940: The intended use is for stimulation of peripheral nerves for diagnostic purposes. The use of devices for other than their FDA cleared intended use is considered as investigational. Such use is only permitted if the Investigational Device Exemption (IDE) guidelines have been followed.

All investigational devices must be labeled in accordance with the labeling provisions of the IDE regulation (§ 812.5) and must bear a label with this statement: "CAUTION Investigational Device. Limited by Federal (or United States) law to investigational use."

6.1.1.2 PREPARATION AND ADMINISTRATION OF STUDY INVESTIGATIONAL PRODUCT

After participants have completed questionnaires and EEG, they will be comfortably seated. The researcher will be thoroughly trained in the safe use of TMS. All researchers administering TMS have written and digital documentation of training. Researchers will be present at all times during stimulation. To monitor side effects of stimulation, a questionnaire will be administered after each stimulation session.

6.1.2 STUDY INTERVENTION DESCRIPTION

Screening: Participants will be recruited from among patients who are seen in neurology clinics at UNC for evaluation and treatment of idiopathic Parkinson's disease. A member of the research team will review data available in Epic for eligibility and recruitment, and flag patients who may qualify for the study. The treating neurologist will also be asked to consider potential participants' eligibility. Once potential participants have been identified, they will be asked in person, over telephone, and/or emailed by our research team to assess their interest in the study, and provide information about the research study. If the potential participant indicates they are interested, the study coordinator or research assistant will set up a time for the potential participant to have a screening research visit. Screening visits may be scheduled in the UNC Neurology clinic, or at the [name] laboratory, depending on convenience for the participant. At the screening visit, the study team member conducting the visit will clearly state that agreement or refusal to participate will in no way influence the patient's care. If the patient does not want to participate, this will be documented in the patient's chart, and the patient will not be contacted in the future about this study. If the patient is interested in participating in the study, the study inclusion and exclusion criteria will be reviewed again with the patient at the study visit. The study will be explained in detail to the potential participant, all questions will be answered to the potential participant's satisfaction, and the study coordinator, research assistant, PI, or co-I will obtain informed consent in person.

Once consent is obtained, the participant will be assigned an anonymous research ID number. Only the study team members will have access to data linking the participant's research data and any PHI. Demographic data will be obtained, including age, sex, concurrent medications, and disease duration. A trained research team member will administer a brief cognitive test (the Montreal Cognitive Assessment or MoCA)⁵⁰, the Movement Disorders Society Unified Parkinson's Rating Scale (MDS-UPDRS)⁵¹, and will obtain orthostatic vital signs.

Stimulation study visits

Clinical Evaluations: The SCOPA-AUT⁵², a validated questionnaire for autonomic symptoms in PD, and the Orthostatic Hypotension Questionnaire (OHQ)⁵³, a validated questionnaire for symptoms of orthostatic

intolerance, will be administered before, and then by telephone one day after, and four days after each stimulation session. The Beck Depression inventory II (BDI-II)⁵⁴, recommended for screening and assessment of depression severity in PD⁵⁵, will be administered before, and then by telephone one day after, and four days after each stimulation. A trained research team member will administer the Movement Disorders Society Unified Parkinson Disease Rating Scale (MDS-UPDRS)⁵¹, a validated rating scale of PD symptom severity, at baseline. Participants will have orthostatic blood pressure measurement with a standard sphygmomanometer cuff before and after each stimulation session. All evaluations will be done with subjects in the “on” medication state with regards to dopaminergic medication dosing. Quantitative EEG (qEEG) recordings will be done before and immediately after each stimulation session. EEG: A high-density EEG net (128 electrodes including electrooculography electrodes; MagStim EGI, Inc.) and two submental electromyography (EMG) electrodes will be applied. Continuous qEEG recording will be performed for 8 minutes while the participant is asked to keep their eyes open and focused on a crosshairs. Sampling rate during the continuous recording will be 1 kHz with Cz as the reference and a channel between Cz and Pz as ground, using an EGI system with SDK AmpServer Pro (Geodesic, Eugene, Oregon). Intermittent theta-burst stimulation: Subjects will undergo iTBS to the mPFC, left DLPFC, and left primary sensory area in a triple cross-over study design. I will use a MagVenture MagPro X100 TMS device with active cooling coil. Stimulation location will be determined using established scalp coordinates for each stimulation location with the “10-20” international coordinate system⁴²⁻⁴⁵. For the mPFC, stimulation will be done at the Fp1 EEG electrode location, which can be calculated as along the midline of the scalp and 10% of the distance from nasion to inion. For left DLPFC, stimulation will be done at the F3 location using the Beam-F3 technique^{46,47}. For the primary sensory cortex, stimulation will be done 1.5cm posterior to the motor hotspot used for intensity calibration. Stimulation will be delivered at 80% active motor threshold. Accelerated iTBS will be performed in the reclined position to reduce symptoms of orthostatic hypotension, with subjects awake and at rest. Subjects will receive bursts of 3 pulses at 50 Hz repeated at 200-msec intervals (5Hz) for two seconds^{48,49}. The two-second trains will be repeated 20 times every 10 seconds (4 minutes total stimulation time), and followed by a 20 minute rest period. This sequence will be repeated 4 times. Behavioral effects of stimulation last at least 36 hours after one stimulation session with this protocol¹. TMS is FDA-approved for the treatment of symptoms of depression, and is a widely-used safe clinical tool.

6.1.3 DOSING AND ADMINISTRATION

During the first stimulation session in the study, participants will receive a motor thresholding procedure in which electrodes are attached to the first dorsal interosseous muscle of the right hand, or another muscle on the hand or arm that is accessible to be targeted by TMS to the motor cortex. The contralateral motor cortex will be targeted by single pulses of TMS with increased stimulator output until a motor evoked potential (MEP), defined as a near-instantaneous increase in muscle activity greater than 200 microvolts, is generated. Next, the intensity of single pulse TMS will be lowered until a MEP is generated on five out of 10 pulses. This is defined as the individual’s motor threshold. If MEP determination of motor threshold is not possible, the researcher will use visible twitches as a proxy for MEP. Participants will receive iTBS at 80% of their motor threshold.

Subjects will undergo iTBS to the mPFC, left DLPFC, and left primary sensory area in a triple cross-over study design. I will use a MagVenture MagPro X100 TMS device with active cooling coil. Stimulation

location will be determined using established scalp coordinates for each stimulation location with the “10-20” international coordinate system⁴²⁻⁴⁵. For the mPFC, stimulation will be done at the Fp1 EEG electrode location, which can be calculated as along the midline of the scalp and 10% of the distance from nasion to inion. For left DLPFC, stimulation will be done at the F3 location using the Beam-F3 technique^{46,47}. For the primary sensory cortex, stimulation will be done 1.5cm posterior to the motor hotspot used for intensity calibration. Accelerated iTBS will be performed in the reclined position to reduce symptoms of orthostatic hypotension, with subjects awake and at rest. Subjects will receive bursts of 3 pulses at 50 Hz repeated at 200-msec intervals (5Hz) for two seconds^{48,49}. The two-second trains will be repeated 20 times every 10 seconds (4 minutes total stimulation time), and followed by a 20 minute rest period. This sequence will be repeated 4 times. Behavioral effects of stimulation last at least 36 hours after one stimulation session with this protocol¹.

A high-density EEG net (128 electrodes including electrooculography electrodes; MagStim EGI, Inc.) and two submental electromyography (EMG) electrodes will be applied. Continuous qEEG recording will be performed for 8 minutes while the participant is asked to keep their eyes open and focused on a crosshairs. Sampling rate during the continuous recording will be 1 kHz with Cz as the reference and a channel between Cz and Pz as ground, using an EGI system with SDK AmpServer Pro (Geodesic, Eugene, Oregon). Collecting EEG with TMS does not pose any additional risk over TMS on its own. EEG electrodes are placed on the scalp to record electrical brain activity. EEG does not involve brain stimulation and is used purely as a neuroimaging tool, posing minimal risk.

6.2 MEASURES TO MINIMIZE BIAS: RANDOMIZATION AND BLINDING

To control for bias, we have decided on a prospective, controlled, triple crossover (three stimulation locations at separate study visits) study design. Participants will be blinded as to stimulation location, and each participant will experience stimulation at all locations. Each participant will have all rating scales performed by the same rater. Potential confounding factors, such as age, disease duration, cognitive function, and overall disease severity will be evaluated and controlled for, as indicated, in the final statistical models.

Stimulation order will be randomized and counter-balanced. Participants are assigned a study ID number and randomized upon signing the informed consent form. Subject ID will be entered into the randomization algorithm by the research assistant. A randomization table will be generated by a computerized script that randomizes and counterbalances by ID, generating an Excel spreadsheet. We will perform complete counterbalancing, there are 6 potential sequences (mPFC-DLPFC-S1, mPFC-S1-DLPFC, DLPFC-mPFC-S1, DLPFC-S1-mPFC, S1-mPFC-DLPFC, S1-DLPFC-mPFC) and a plan for 48 participants. Every effort will be made to completely counterbalance our sample. Thus effects of stimulation order will be minimized.

Treatment Assignment Procedures: Participants will receive stimulation to the medial prefrontal cortex, the dorsolateral prefrontal cortex, and the primary sensory cortex. The order of stimulation will be randomized and counterbalanced. Randomization will be performed using a script that generates a

spreadsheet. Randomization will be done after the screening visit is completed, before initiation of stimulation sessions.

6.3 STUDY INTERVENTION COMPLIANCE

Compliance is determined by completion of all three stimulation sessions.

6.4 CONCOMITANT THERAPY

For this protocol, a prescription medication is defined as a medication that can be prescribed only by a properly authorized/licensed clinician. Medications to be reported in the Case Report Form (CRF) are concomitant prescription medications, over-the-counter medications and supplements. Information about concomitant medications will be collected in pre-screening procedures, at the screening visit, and at each stimulation visit. Excluded medications include antihypertensive medications, diuretics, and alpha-blocking medications.

6.4.1 RESCUE MEDICINE

N/A

7 STUDY INTERVENTION DISCONTINUATION AND PARTICIPANT DISCONTINUATION/WITHDRAWAL

7.1 DISCONTINUATION OF STUDY INTERVENTION

Discontinuation from stimulation does not mean discontinuation from the study, and remaining study procedures should be completed as indicated by the study protocol. If a clinically significant finding is identified (including, but not limited to changes from baseline) after enrollment, the investigator or qualified designee will determine if any change in participant management is needed. Any new clinically relevant finding will be reported as an adverse event (AE).

The data to be collected at the time of study intervention discontinuation will include the following:

- All remaining study questionnaires

7.2 PARTICIPANT DISCONTINUATION/WITHDRAWAL FROM THE STUDY

Participants are free to withdraw from participation in the study at any time upon request.

An investigator may discontinue or withdraw a participant from the study for the following reasons:

- Significant study intervention non-compliance
- If any clinical adverse event (AE), laboratory abnormality, or other medical condition or situation occurs such that continued participation in the study would not be in the best interest of the participant
- Disease progression which requires discontinuation of the study intervention
- If the participant meets an exclusion criterion (either newly developed or not previously recognized) that precludes further study participation

- There are factors that, in the opinion of the PI, would place the participant at increased physical or psychological risk, or preclude the participant's compliance or completion of the study

The reason for participant discontinuation or withdrawal from the study will be recorded on the Case Report Form (CRF). Subjects who sign the informed consent form and are randomized but do not receive the study intervention may be replaced. Subjects who sign the informed consent form, and are randomized and receive the study intervention, and subsequently withdraw, or are withdrawn or discontinued from the study, will not be replaced.

Safety data will be collected on any participant that is discontinued due to an AE or SAE. Every effort will be made to complete protocol-specific follow up procedures if possible. If voluntary withdrawal occurs, the participant will be asked to continue scheduled evaluations and complete an end-of-study evaluation. Medical and psychological follow up will be coordinated by the research team as described in this protocol. The researcher will make a note to file for all withdrawals.

7.3 LOST TO FOLLOW-UP

A participant will be considered lost to follow-up if he or she fails to return for 2 scheduled visits and is unable to be contacted by the study site staff.

The following actions must be taken if a participant fails to return to the clinic for a required study visit:

- The site will attempt to contact the participant and reschedule the missed visit within two weeks and counsel the participant on the importance of maintaining the assigned visit schedule and ascertain if the participant wishes to and/or should continue in the study.
- Before a participant is deemed lost to follow-up, the investigator or designee will make every effort to regain contact with the participant (where possible, 3 telephone calls and, if necessary, a certified letter to the participant's last known mailing address or local equivalent methods). These contact attempts should be documented in the participant's medical record or study file.
- Should the participant continue to be unreachable, he or she will be considered to have withdrawn from the study with a primary reason of lost to follow-up.

8 STUDY ASSESSMENTS AND PROCEDURES

8.1 EFFICACY ASSESSMENTS

8.1.1 SELF-COMPLETED QUESTIONNAIRES

Participants will fill out the following questionnaires:

- Scales for Outcomes in Parkinson's – autonomic (SCOPA-AUT) – Autonomic self-completed symptom questionnaire, contains 21 questions plus 2 questions that are specific for men and 2 specific for women; therefore every participant will answer 23 questions⁵². Each item score range is 0-3 for severity of symptoms. Score range is 0-69 points, where higher points

indicates higher burden of symptoms. This will be completed prior to each stimulation session in person, and over telephone one day after and 4 days after stimulation

- Orthostatic Hypotension Questionnaire (OHQ)⁵³ - a validated questionnaire for symptoms of orthostatic intolerance, contains 10 questions. Each question is scored out of 10 possible points. Score range is 0-100, where higher points indicates higher burden of symptoms. This will be completed prior to each stimulation session in person, and over telephone one day after and 4 days after stimulation
- Beck Depression inventory II (BDI-II)⁵⁴ - recommended tool for screening and assessment of depression severity in PD⁵⁵. Consists of 21 questions, each question ranges in score from 0-3 points. Score range is 0-63, where higher points indicates higher burden of symptoms. This will be completed prior to each stimulation session in person, and over telephone one day after and 4 days after stimulation
- MDS - Unified Parkinson's disease Rating Scale (MDS-UPDRS) parts 1b and 2 – Validated clinical tool, it is a rating scale for disease severity in Parkinson's disease. Part 1b is the Non-Motor Aspects of Experiences of Daily Living, and consists of 7 questions, each worth 0-4 points. Score range is 0-28 points. Part 2 is the patient ADL questionnaire and contains 13 questions⁵¹, each worth 0-4 points. Score range is 0- 52 points, This will be completed at the screening visit only.
- Freezing of Gait questionnaire– Assesses symptoms of freezing of gait in Parkinson disease. Contains 6 questions, each scored 0-4⁵⁶. Score range is 0-24, with higher score meaning higher burden of symptoms. This will be completed at the screening visit only
- Epworth sleepiness scale – Assesses symptoms of fatigue and sleepiness. Contains 8 questions, each scored 0-4.⁵⁷ Score range is 0-24, with higher score meaning higher burden of symptoms. This will be completed at the screening visit only.
- REM sleep disorder screening questionnaire – Screening questions about symptoms of REM sleep behavior disorder. This questionnaire contains 10 questions, one question has 4 parts⁵⁸. Each question and question part is scored 0-1. Score range is 0-13, with higher score indicating higher burden of symptoms. This will be completed at the screening visit only

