There is a very low theoretical likelihood that stimulation of neuronal circuits can lead to epileptic discharges. To minimize this risk, we will exclude potential participants with personal history of epilepsy or risk factors for epilepsy. If abnormalities on EEG or a seizure is witnessed during the course of the study, a referral will be made to the UNC Department of Neurology for follow up, and/or the participant's treating neurologist will be notified. In the unlikely event that a seizure with loss of consciousness is witnessed during the course of the study, the participant will be instructed not to operate a motor vehicle until cleared by the Department of Motor Vehicles (DMV).

One of the scales that will be administered assess symptoms of depression (BDI-II questionnaire). Upon receiving this questionnaire, the research coordinator will check the scoring for this assessment. If the patient scored in the "severe" range (>28 points), the PI will be notified, and appropriate immediate referrals for care will be made per the patient's preference. The participant's treating neurologist or primary care physician will be immediately notified via a phone call. 911 will be called in the event that a participant is threatening to hurt themselves or others.

Hearing loss is a potential risk of TMS. This is a rare and moderate to severe risk. To protect against hearing loss, ear plugs are worn by the participant and by the technical operator during stimulation sessions.

There have been rare reports of mood episode switches in people with Bipolar disorder after iTBS (from depressed mood to mania or hypomania). This is a rare but potentially severe.

Other potential risks associated with participation in this study include:

- Scalp irritation due to application of the electroencephalogram electrodes to the scalp. This is infrequent and mild.
- Headache and dizziness are rare and mild
- Muscle tightness and twitching during stimulation are very common and mild

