9.1 STATISTICAL HYPOTHESES

Aim 1

H_0 : Mean change in Frontal midline theta power on electroencephalogram after iTBS to the medial prefrontal cortex will be equal to FMT changes after dorsolateral prefrontal cortex stimulation and stimulation of S1.

H_1 : Mean change in Frontal midline theta power on electroencephalogram after iTBS to the medial prefrontal cortex will be greater than FMT changes after dorsolateral prefrontal cortex stimulation and stimulation of S1.

Primary Outcome Measure: The primary objective will test the degree of change in frontal midline theta (FMT) power (μ) before and after iTBS at each stimulation location. The primary outcome measure will be FMT power. *Aim 2a Hypothesis:*

H_0 : There is zero correlation between severity of autonomic dysfunction symptoms at baseline before stimulation with frontal midline theta power at baseline on electroencephalogram.

H_1 : There is a negative correlation between severity of autonomic dysfunction symptoms at baseline before stimulation with frontal midline theta power at baseline on electroencephalogram.

Aim 2b Hypothesis:

H_0 : There is no correlation between severity of depression symptoms at baseline before stimulation with frontal midline theta power on electroencephalogram at baseline.

H_1 : There is negative correlation between depression symptoms at baseline before stimulation with frontal midline theta power on electroencephalogram at baseline.

- Primary Outcome Measures: We will test associations between autonomic symptoms, depression symptoms, and FMT power at baseline before stimulation, where the FMT power (μ) will be the primary outcome measure.

Exploratory objectives

Aim 3 Hypothesis:

H_0 : Change in SCOPA-AUT and OHQ will be zero one day after stimulation and 4 days after stimulation compared to pre-stimulation.

H_1 : Change in SCOPA-AUT and OHQ will be less than zero one day after stimulation and 4 days after stimulation.

- Primary Outcome Measures: Change in SCOPA-AUT and OHQ from before to one day and 4 days after stimulation

Aim 4 Hypothesis:

H_0 : Change in BDI-II will be zero one day after stimulation and 4 days after stimulation compared to pre-stimulation.

H_1 : Change in BDI-II will be less than zero one day after stimulation and 4 days after stimulation.

- Primary Outcome Measure: Change in BDI-II before to one day and 4 days after stimulation

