10.1.10 DATA HANDLING AND RECORD KEEPING

10.1.10.1 DATA COLLECTION AND MANAGEMENT RESPONSIBILITIES

Data collection is the responsibility of the study personnel under the supervision of the PI. The investigator is responsible for ensuring the accuracy, completeness, legibility, and timeliness of the data reported.

All source documents should be completed in a neat, legible manner to ensure accurate interpretation of data.

All questionnaires will be in paper format and will be collected by the study coordinator in person at the study visit or via mail as described above. In order to maintain privacy and confidentiality regarding subject participation, there will be no more than one printed copy of a spreadsheet with subject ID numbers linked to their identifiers, which will only consist of name, medical record number, study ID number, age, and date of birth. This spreadsheet will be kept in the office of study personnel, within a locked cabinet with multiple layers of physical security to enter this office including necessary UNC employee badge access. An electronic copy of this form will be stored in a HIPAA compliant fashion, as detailed below. Once the study has ended, only codes shall remain, and the aforementioned spreadsheet shall be destroyed in a HIPAA-compliant fashion. This will not directly affect any UNC medical records.

Consent forms will be scanned and loaded into Epic, and a copy will be saved for our records on the UNC School of Medicine Neurology secure server, which is HIPAA compliant and password-secured. The original hard copy will be stored in a locked office, inside a locked office cabinet, located in the Physician's office building. The participants will receive a copy of the signed consent form for their own personal records.

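### SCOPA-AUT, OHQ and BDI-II move from in person before stimulation to telephone afterwards, so the Aim 3 and 4 change from baseline cannot be told apart from a mode shift; the contrast with S1 can, if the shift is the same at every site

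*Combined protocol and SAP*

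**What the plan says.** Section 8.1.1 covers self-completed questionnaires and opens with "Participants will fill out the following questionnaires". For SCOPA-AUT, OHQ and BDI-II it repeats one instruction: "This will be completed prior to each stimulation session in person, and over telephone one day after and 4 days after stimulation". Section 6.1.2 agrees on the route, saying of the BDI-II that it "will be administered before, and then by telephone one day after, and four days after each stimulation". The Schedule of Activities (1.3) places all three scales at the stimulation visits and at the telephone visits 1 and 4 days later.

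Section 10.1.10.1 reads differently: "All questionnaires will be in paper format and will be collected by the study coordinator in person at the study visit or via mail". It refers back to an earlier description, but no earlier section describes mailing questionnaires. The synopsis only lists mailings among the types of contact.

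The Aim 3 alternative in 9.1 is "Change in SCOPA-AUT and OHQ will be less than zero one day after stimulation and 4 days after stimulation", and Aim 4 has the same form for BDI-II. Section 9.4.1 plans linear mixed models for both aims, with stimulation location by time as factors and age and disease duration as covariates. Mode of administration does not appear. Section 4.2 names S1 as the control site.

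**The concern.** Every pre-stimulation score is obtained in person and every post-stimulation score by telephone. Mode and time are therefore the same variable in the data, and no covariate can separate them. The scales ask about mood and about autonomic symptoms that include bladder, bowel and sexual function. People may answer such items differently when speaking to study staff than when writing on a form. Any such difference would go straight into the change from baseline, which is the quantity the Aim 3 and 4 hypotheses are written about.

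The conflict with 10.1.10.1 adds a second problem. Staff could reasonably telephone for some contacts and use mailed forms for others, which would add noise and leave the true completion date of a day-1 or day-4 answer uncertain. The route also affects the BDI-II severity check in 2.3.1, which starts on receipt: "Upon receiving this questionnaire, the research coordinator will check the scoring for this assessment". The sections should therefore agree on when and how the form is received.

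**Working it through.** **Inputs.** N = 48 planned, with power quoted at N = 45 (9.2). Alpha is 0.05 (9.2). The alternative is change below zero (9.1). The effect size for the exploratory aims is g = 1.0 (0.3 to 1.7) with 2 predictors (9.2). The size and direction of a mode shift are not in the documents. I write it as m, in SD of the change score, and show a range.

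**1. The plan's own figure.** Section 9.2 gives power 0.95 (0.26 to 1.00). Take f² = (g/2)², noncentrality √(f² × 45) and df = 45 − 2 − 1 = 42, with a one-sided t test of one coefficient:

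- g = 1.0: f² = 0.25, noncentrality √11.25 = 3.35, power 0.951
- g = 0.3: f² = 0.0225, noncentrality √1.0125 = 1.01, power 0.256
- g = 1.7: f² = 0.7225, noncentrality √32.51 = 5.70, power 1.000

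The figure is reproduced. A two-sided test gives 0.906 and an overall F test on 2 predictors gives 0.834, so the quoted power matches a directional test, as do the hypotheses. The power figure is not in error on this point, but it makes no allowance for a mode shift.

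**2. What each comparison estimates.** Let d be the stimulation effect at a site and m the telephone-minus-in-person shift.

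- Before/after change at mPFC: d(mPFC) + m. The shift stays in.
- Difference in change, mPFC minus S1: [d(mPFC) + m] − [d(S1) + m] = d(mPFC) − d(S1). A shift common to both sites drops out.

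**3. Size for the uncontrolled before/after comparison.** This is a one-sided one-sample t test on change, one session, N = 48, df = 47, no true effect. The shift is towards fewer reported symptoms, and the noncentrality has magnitude m√48 = 6.93m.

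| m | 6.93m | rejection rate |
|---|---|---|
| 0 | 0 | 0.050 |
| 0.1 | 0.69 | 0.168 |
| 0.2 | 1.39 | 0.390 |
| 0.3 | 2.08 | 0.657 |

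At N = 45 the rates for 0.1, 0.2 and 0.3 are 0.162, 0.373 and 0.632.

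**4. Shift in the other direction.** For a true change of −0.5 SD at N = 48, power without a shift is 0.96. An upward shift of 0.2 SD leaves a net −0.3 SD and power 0.66. An upward shift of 0.3 SD leaves a net −0.2 SD and power 0.39.

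**5. Check of the cancellation.** In 20,000 simulated trials with N = 48, no true effect and the same shift at every site, the two-sided test of mPFC minus S1 change rejected in 5.1%, 5.0% and 5.2% of trials for m = 0, 0.3 and 0.5. The simulation drew changes independently across sites.

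**The case against.** The strongest reply is that the design already contains the remedy. The same switch of mode happens at all three sites in the same participants, who are blinded to location (6.2), and 9.4.1 plans location-by-time models with S1 as control. A common shift falls on the time effect and leaves the between-site contrast alone. This stands. A reader might infer that the documents give no means of separating mode from effect, and that inference is not supported. The protection does require an equal shift at every site. Section 4.1 says study personnel know the location, the plan does not say whether callers do, and 6.2 states: "Each participant will have all rating scales performed by the same rater". A caller who knows the site could in principle produce a site-dependent shift, but nothing in the documents shows that this would happen.

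A second reply is that the t test in the illustration is not the planned analysis, and this also stands. The 17% to 66% figures describe what happens if change from baseline is tested alone, as the hypotheses are worded. They are not the error rate of the planned mixed model. An uncontrolled before/after comparison would also remain open to placebo response and regression to the mean, even with one mode throughout.

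Third, the contradiction may be partly wording. Section 10.1.10.1 also says clinical data are recorded on paper and then computerised, so telephone answers written down by staff would count as paper. That does not explain the mention of mail. Finally, 6.1.2 says the scales are administered before stimulation, so private completion at baseline rests on 8.1.1 alone. The move from in person to telephone holds under either reading.

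**Conclusion.** The point holds for the Aim 3 and 4 hypotheses as worded. Mode is aliased with time, and a change below zero cannot be attributed to stimulation rather than to the switch to telephone. The illustrative size is a rejection rate of 17%, 39% or 66% in place of 5% for shifts of 0.1, 0.2 or 0.3 SD. If the shift runs the other way, power for a true −0.5 SD change falls from 0.96 to 0.66 (0.2 SD) or 0.39 (0.3 SD). Both depend on an assumed shift and an uncontrolled one-session test.

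The planned contrast with S1 is protected provided the shift is equal across sites. It would be wrong to read this as a threat to the primary results: Aim 1 uses EEG power and Aim 2 uses pre-stimulation scores only. The inconsistency between 8.1.1 and 6.1.2 on one side and 10.1.10.1 on the other is real and should be resolved whatever view is taken of the bias. It is worth acting on because the change is cheap now and the aliasing cannot be undone in the analysis later.

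**What to change.** 1. Use the same written, self-completed form at every time point. At each stimulation visit, give the participant dated copies of the three scales for day 1 and day 4, to be completed before the call already scheduled. The call records the written answers, so scores are available that day, and the form comes back by mail or at the next visit. Align 6.1.2, 8.1.1 and 10.1.10.1 with this, and make clear which event counts as receipt of the BDI-II for 2.3.1.
2. In 9.1 and 9.4.1, state the between-site difference in change (location by time, mPFC and DLPFC each against S1) as the Aim 3 and 4 test. Say that before/after change alone will not be interpreted as a stimulation effect.

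The cost is printed forms, return envelopes and edits to the text, with no added contacts. Some forms will come back late. Answers are still spoken to staff on the call, so any reluctance to disclose is reduced rather than removed. If the sponsor keeps the telephone route, the second change should still be made and the mode switch reported as a limitation.
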